7. RESEARCH QUESTION AND OBJECTIVES

The aim of this DUS is to determine indications for use among REVOLADE users within several EU countries utilizing real-world data obtained in medical records.

The objectives of the study are:

- To document REVOLADE utilisation patterns, classified according to the medical conditions and the patient age categories for which REVOLADE is being prescribed in selected European countries
- To characterize the patients who are prescribed REVOLADE in routine clinical practice.

8. RESEARCH METHODS

8.1. Study Design

This is a multi-national, multi-center study involving the retrospective review of approximately 300 to 450 patient medical records from selected European countries including France, Germany, Spain, and other relevant selected European Union (EU) Member States (see Section 8.2) with each country contributing approximately six or seven sites. It is estimated that 18 to 21 hospital or office based sites overall where prescribers of REVOLADE have been identified and medication records exist, will be targeted for recruitment. The investigators will be queried to identify REVOLADE treated patients during the periods of interest. To the extent possible, a selection of sites representative of the country prescription volumes will be enroled.

Medical records of all consecutive patients treated with REVOLADE, irrespective of indication, dose, treatment duration or any patient characteristic will be retrospectively reviewed to confirm eligibility.

Medical records will be reviewed for data from REVOLADE first prescription. This study involves no intervention, and will not impact the usual medical care or affect the treatment of patients. Thus, the study will reflect a real world medical practice without the potential for prescriber response bias, which may occur in prospective studies (i.e., the Hawthorne Effect) (Mangione-Smith, 2002).

The study overview is provided in the figure below:

[figure not shown]

Figure 1 REVIEU Study Overview

In Figure 1 EU approval for first indication (March 2010) refers to the approval of REVOLADE: "Revolade is indicated for adult chronic immune (idiopathic) thrombocytopenic purpura (ITP) splenectomised patients who are refractory to other treatments (e.g. corticosteroids, immunoglobulins). Revolade may be considered as

Page 116 WEUKBRE7133

second line treatment for adult non-splenectomised patients where surgery is contraindicated."

EU approval for second indication refers to "Revolade is indicated in adult patients with chronic HCV infection for the treatment of thrombocytopenia, where the degree of thrombocytopenia is the main factor preventing the initiation or limiting the ability to maintain optimal interferon-based therapy."

8.2. Setting

The REVOLADE DUS will include approximately 300 to 450 patients being treated with REVOLADE at approximately 18-21 hospital/ward or office based sites in selected EU Member States. France, Germany and Spain are the primary targeted countries, based on the most frequent REVOLADE use approximated from IMS prescription sales data. To meet the recruitment goal, additional EU country(ies) and sites may be added based on multiple factors including use of REVOLADE (compared to use approximated by sales data), available prescription data, and favourable regulatory environment to conduct observational studies.

To avoid overrepresentation of any individual sites or countries, recruitment may be capped during the study at site or country level.

8.2.1. Inclusion Criteria

To be enrolled into the study, patients must meet the following criteria:

- Documented past treatment with REVOLADE between the period immediately after first approval/launch and September 2014 (i.e., dispensed at least once by the pharmacy and patient received at least one dose) for whatever reason
- Patient (or a legal representative) has provided a written informed consent to participate in the study

8.2.2. Exclusion Criteria

• Patients who participated or are participating in a randomized REVOLADE clinical trial

8.2.3. Study Duration

The eligibility period begins within the period immediately after REVOLADE has been launched in a given country (for instance, REVOLADE launch dates for the chronic ITP indication are in Germany, France and Spain, April 2010, January 2011, and December 2010, respectively) until the index date chosen as the start date of data abstraction i.e., September 2014 (Figure 1).

The observational period for each patient is the interval between the first dose of REVOLADE and the last dose if discontinued before September 2014. If a patient stops and re-starts REVOLADE during the observation period, all repeated treatment intervals will be captured. Also, if the patient is still on REVOLADE at the end of the study period, September 2014, then the observation period is between first dose and September 2014.

The planned duration of the study is approximately 14 months after the inclusion of the first patient. This period takes into account 8 months of data collection and study start-up and a 6 month period between last patient in and final study report.

GSK will closely monitor inclusion rates. If projected recruitment rates indicate that patient targets may not be achieved in the planned recruitment period, consideration will be given to extending the recruitment period, initiating additional sites within the three existing countries, and/or expanding the study into additional EU countries.

8.2.4. Site Selection

The study will be implemented at approximately 18- 21 sites in selected countries in the EU (six or seven sites per country) by selecting sites that are geographically dispersed to best represent different practices across regions/provinces within the selected EU Member States. Also, selection of study sites will be determined at the country level in order to obtain a representative sample of sites reflective of the treatment patterns within each country. Site qualification and selection criteria will include: type of physician/hospital, geographic location (e.g., rural, urban), practice setting (clinics, academic setting, and reference centre), capture area, estimated eligible patient availability, number of patients seen in previous year, availability and number of eltrombopag pharmacy records), and staffing availability.

The Study will target a representative sample of physicians who prescribe REVOLADE, irrespective of the indication. These include hematologists, oncologists, virologists, hepatologists, internal medicine and other specialists from the hospital or office based setting. The data collected in the Study will be used to determine the characteristics of patients for whom REVOLADE is prescribed and to understand if it is being prescribed in accordance with the product labelling.

The site and investigator identification, selection and recruitment process will be detailed in the Site Recruitment Plan document, which will be developed at study start-up. This document will describe the process for site identification, site recruitment process with flow chart, site qualification process via the study specific site qualification questionnaire. In addition, this document will describe the process how to contact and conduct follow-up activities of identified sites and investigators. Potential risks to the plan will be identified early in its development to ensure that proper risk mitigation measures are put in place to ensure achievement of site enrolment objectives.

Given the prescription rates of REVOLADE in EU Member States, a multi-faceted approach will be taken to identify potential sites and investigators. This approach will include the review of the CRO internal database, and the collaboration with GSK local operating companies on most suitable sites and market research of prescription data. A Site Qualification Survey will be administered to all identified potential sites requesting information on their location, practice (specialty, type), patients treated with REVOLADE within their practice (past and current number, treating duration) and dispensing system (not specifically related to the main objective of the DUS).

Based on responses from the Site Qualification Survey, a probability sample of REVOLADE prescribers will be selected, using a stratified unbiased random approach to produce a representative set of sites. This will ensure both representativeness and comprehensiveness of the sample in terms of types of REVOLADE prescribers. The general aim of this approach is to minimize biases such as for instance the recruitment of prescribers from academic versus community hospitals.

In order to ensure adequate numbers of participating sites, the Potential Prescriber List will include three times the number of sites required for the study. Depending on the participation rate and enrolment rates for the Study, the Back-up Potential Prescriber List of study sites may be contacted. To maximize representativeness at the study level, quota sampling of the remaining sites from the list will be performed.

The dispensing system of REVOLADE in the selected Member States is fully described in the ANNEX 2.

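### Filling back-up sites by quota sampling would make the site sample partly non-probability, so representativeness could not be claimed from the random draw alone

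*Protocol*

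**What the plan says.** Protocol section 8.2.4 sets out site selection in four steps.

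- **Frame.** Candidate sites come from "the review of the CRO internal database, and the collaboration with GSK local operating companies on most suitable sites and market research of prescription data". Every candidate identified then receives a Site Qualification Survey.
- **Random draw.** From the survey responses, "a probability sample of REVOLADE prescribers will be selected, using a stratified unbiased random approach to produce a representative set of sites". The protocol adds: "This will ensure both representativeness and comprehensiveness of the sample in terms of types of REVOLADE prescribers". The one bias it names as an example is the recruitment of academic versus community hospital prescribers.
- **Reserve.** To secure enough sites, "the Potential Prescriber List will include three times the number of sites required for the study". Use of the back-up list is conditional: "Depending on the participation rate and enrolment rates for the Study, the Back-up Potential Prescriber List of study sites may be contacted".
- **Remaining sites.** With representativeness across the whole study as its declared purpose, the protocol says that "quota sampling of the remaining sites from the list will be performed".

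The same section leaves process detail to a Site Recruitment Plan, which is not part of the protocol.

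**The concern.** Two methods with different properties are joined under one claim. A stratified random draw gives each listed site a known chance of selection, and within a stratum that chance does not depend on how convenient the site is. A quota step sets the number of sites per cell and leaves the choice within the cell open unless the plan says otherwise. This protocol does not say otherwise. Sites that enter by quota have unknown selection probabilities, so the representativeness attached to the random draw does not extend to them.

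The study is meant to describe to the EMA how the drug is used, including how much use is outside the label. If label adherence differs between sites of the same type, for instance by experience with the drug, selective choice within a cell would move the pooled proportion. The planned precision would give no sign of it.

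**Working it through.** **1. The plan's own precision figure.** Section 8.5.1 gives 2.1 points for 5% off-label use with 400 patients. The formula is half-width = 1.96 × √(p(1−p)/n). With p = 0.05 and n = 400 it gives 1.96 × √(0.05 × 0.95 / 400) = 0.0214, an interval of 2.9% to 7.1%. The figure reproduces, as do the other cells of Table 1. The formula treats patients as a simple random sample, so it contains nothing about how sites were chosen.

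**2. How many sites are involved.** Section 8.2.4 plans 18 to 21 sites and a list three times that size: 3 × 18 = 54 to 3 × 21 = 63. Each participating site is 1/21 to 1/18 of the sites, or 4.8% to 5.6%. Section 8.2.5 allows up to 50 records per site, so one site could supply 50/400 = 12.5% of 400 patients. The protocol does not say how many sites would come from the quota step.

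**3. What the quota step keeps and what it loses.** If the cells are prescriber types, the quota holds the mix of types, which is what the assurance in section 8.2.4 refers to. It does not protect against selective choice between two sites of the same type. A random order within the stratum would do both.

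**4. How large a shift could be.** Let f be the share of patients from quota-chosen sites. Let d be the difference in off-label proportion between those sites and sites drawn at random from the same stratum and list. The shift in the pooled estimate is f × d. The protocol gives neither input, so the values below are assumptions that show the range and are not estimates.

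| f | d = 2 points | d = 5 points | d = 10 points | d at which the shift equals 2.1 points |
|---|---|---|---|---|
| 0% | 0 | 0 | 0 | none |
| 10% | 0.2 | 0.5 | 1.0 | 21 |
| 25% | 0.5 | 1.25 | 2.5 | 8.4 |
| 33% | 0.7 | 1.7 | 3.3 | 6.3 |
| 50% | 1.0 | 2.5 | 5.0 | 4.2 |

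(Shifts and d are in percentage points; the last column is 2.1 / f.)

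The large entries need a large d. Section 8.5.1 plans around 2% to 5% off-label use. If randomly drawn sites have 5%, quota sites can be at most 5 points lower, so the largest downward shift at f = 50% is 0.5 × 5 = 2.5 points. At 2% it is 0.5 × 2 = 1 point. A 5-point upward shift needs quota sites at 15%.

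**5. Whether another safeguard covers it.** The screening log in section 8.2.5 records patients within participating sites. Section 8.9 discusses enrolment bias at patient level. Neither shows which sites declined or how substitutes were picked.

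**The case against.** The strongest reply is that the quota step is conditional and limited. The back-up list may never be used, the primary list already has a threefold reserve, and sites drawn at random stay in the sample. The assurance concerns types of prescriber, and quotas set on those types would preserve that balance. The Site Recruitment Plan might also specify random choice within cells. The first two arguments stand and limit the point to the share of sites added by quota. The third stands only in part: the unseen plan may repair the method, but the protocol has already named it as quota sampling.

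A reader might infer that the quota step undoes the random sample altogether, or that cells would be filled with whichever sites are easiest to recruit. The protocol supports neither. The random part remains, and the text is silent on choice within a cell. Nor are sponsor-known or well-staffed sites peculiar to the quota step. The whole frame draws on the sponsor's local companies and the CRO database, and staffing is among the selection criteria for every site. For the same reason the random draw was never the full basis for representativeness.

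A reader might also compare quota sites with the sites they replace and read the result as the cost of quota sampling. That comparison includes bias from refusals, which random replacement would not remove.

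**Conclusion.** The point holds in a limited form. Section 8.2.4 describes a probability sample and then names a non-probability method for the remaining sites. If that method is used, the final sample is partly non-probability, and representativeness cannot be claimed from the random draw alone. What is lost is protection against selective choice within a cell, for the quota share of sites only.

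No bias can be computed from the protocol. Under the assumed inputs, the effect runs from nothing to more than the stated 2.1-point half-width; the upper end needs both a high back-up share and a site difference that is large beside the 2% to 5% planned for. The case for change therefore rests on the inconsistency and on a better method being available at almost no cost, not on a demonstrated shift. It assumes that the Site Recruitment Plan does not already require random choice within cells.

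**What to change.** - Before any site is contacted, put the Potential Prescriber List and the back-up list in random order within each stratum, and keep a record of that order.
- Replace a declining or non-enrolling site with the next site on the order in the same stratum. This keeps the balance that quotas offer and restores random choice within the stratum. The reference to quota sampling can then be deleted.
- Report, by stratum, the sites approached, the sites participating and the number of replacements. Random replacement does not remove bias from refusals, so a reader needs these counts.
- In section 8.2.4, change *will ensure* to *aims at*, since the frame and the refusals limit representativeness whichever replacement rule is used.

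The cost is one random ordering of lists that the plan already requires, and a short table in the report. The downside is that replacement may take slightly longer than approaching a site that is ready to start.

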8.2.5. Patient Enrolment

Since the purpose of this study is to evaluate routine clinical use of REVOLADE, patients will be identified based on the prescription of REVOLADE rather than on a specific diagnosis or condition.

The study population will consist of patients who have been prescribed REVOLADE for whatever reason according to the data retrieved in the medical records, provided they gave informed consent, had not or were not currently participating in a REVOLADE clinical trial, and used REVOLADE within the time period defined below. The medical records of all patients treated with REVOLADE in a participating centre will be reviewed for inclusion in this retrospective study, until the overall target number of at least 300 patients has been reached, irrespective of indication, medical condition, dose and treatment duration.

Patients are eligible for inclusion in study if their first prescription of REVOLADE was given between the period immediately after REVOLADE launch date and the start date for data abstraction i.e., September 2014. Patients who have been first prescribed REVOLADE after September 2014 will not be included in the study in order to ensure that study procedures do not influence prescribing practices. Informed consent will be

obtained as per country-specific regulations. Assuming the country-based first launched dates of REVOLADE in its initial chronic ITP indication (see Figure 1), the eligibility periods in the three selected countries thus span between January 2011 and September 2014 for France, April 2010 and September 2014 for Germany and December 2010 and September 2014 for Spain.

The earliest launch date for the chronic HCV-associated thrombocytopenia indication in these countries can be no sooner than September 2013, corresponding to the date it was approved by the European Commission. Considering that approval of HCV-associated thrombocytopenia indication was just recently, the number of expected HCV-associated thrombocytopenia patients therefore will be very small.

It is expected that approximately six or seven sites will be identified per country, and that up to 50 medical records will be abstracted at each site accounting for a total of 300 to 450 patients for the study.

To assess the representativeness of the sampled patient population, a screening log of all patients treated with REVOLADE will be maintained by the site, including birth year, gender and whether the patient participated in the DUS or not during the eligibility period. For patients who did not participate in the DUS, the reasons for non-participation will be documented on the screening log.

8.2.6. Patient Withdrawal

Patients may withdraw consent and discontinue participation from the DUS at any time, with no effect on their medical care or access to treatment. If a patient is withdrawn prior to completing the study, any known reason for withdrawal should be documented in the electronic case report form (eCRF). All information already collected as part of the study will be retained for analysis; however, no further efforts will be made to obtain or record additional information regarding the patient.

8.3. Variables

An eCRF will be used to collect study data.

8.3.1. Site Questionnaire

The following data will be collected regarding the site and prescribing physician:

- Type of setting (Community hospital, Academic/medical center, office based, etc)
- Physician specialty prescribing REVOLADE (hematologist, oncologist, etc)

8.3.2. REVOLADE General Information

The following data will be collected for all patients enrolled:

WEUKBRE7133

Page 120

• Date of informed consent.

The following data will be collected from the medical records for all patients enroled:

- Demographics:
 - o age at time of first REVOLADE prescribing dose
 - o gender
 - o race/ethnicity (where allowed by local regulation)
- Diagnosis of chronic ITP and date (if medical record data available, will record the disease phase as 'acute' or 'chronic' ITP specifically or just 'ITP', duration of ITP if available)
- Diagnosis of HCV and date; information on previous treatment with antiviral therapy
- Diagnosis of other conditions and date
 - o Hematologic malignancies (AML, MDS, other leukemia, lymphoma, etc)
 - o Aplastic anemia and bone marrow failure
 - o Other
- Medical history for applicable conditions and current medical conditions
 - Surgery (i.e., splenectomized or not)
 - Comorbidities that may be contraindications for surgery (anemia, hyperbilirubinemia, neutropenia, leukopenia, pancytopenia, pneumonia, and others)
 - o Pregnancy status
 - o Non haematological malignancy and type
 - o Comorbidities:
 - Cardiovascular diseases
 - Pulmonary Arterial Hypertension
 - Hypertension
 - Diabetes
- Treatment(s) preceding REVOLADE prescription:
 - Type (corticosteroids, immunoglobulins, cytokines, ribavirin, peginterferon, etc.)
 - Date of treatment initiation
 - Dose and duration
- Concomitant treatment(s) initiated with REVOLADE:
 - Type (corticosteroids, immunoglobulins, cytokines, ribavirin, peginterferon, etc.)
 - o Date of treatment initiation
 - Dose and duration
- All platelet counts (x10⁹/L) at the time of primary medical condition, at initiation of REVOLADE, and dates, and resulting in dose change, by dose

Page 121 WEUKBRE7133

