6. RATIONALE AND BACKGROUND

6.1. Background

Chronic primary immune thrombocytopenia (ITP)

Chronic primary ITP is an acquired immune mediated disorder characterized by isolated thrombocytopenia, defined as a peripheral blood platelet count less than 100×10^9 /L, the absence of any underlying cause, and lasting for more than 12 months (Rodeghiero, 2009).

In Europe, adult ITP has an incidence range of 1.6 to 3.9 cases per 100,000 person-years with increasing incidence with older age. Estimates of prevalence range widely from 9.5 to as high as 189.3 per 100,000 population; prevalence is similar amongst men and women, except in the mid-adult years (i.e., 30-60 years of age), when the disease is more prevalent in women (Deane, 2010).

Diagnosis of ITP is one of exclusion, when the history, physical examination, complete blood count and examination of peripheral blood smear do not suggest other etiology for the thrombocytopenia. Physical examination is typically normal apart from signs of bleeding and the peripheral blood count reveals isolated thrombocytopenia and normal red cell and white cell indices. If significant bleeding occurs there may be anemia proportional to the degree of bleeding with possible iron deficiency. Peripheral blood smear typically shows platelets normal to large in size with no abnormalities seen in red and white cell morphology. Bone marrow examination is currently not routinely conducted in patients with typical ITP presentations, but reserved for selected cases such as those with an atypical presentation.

Guidelines and consensus documents generally recommend clinical intervention in adults when platelet counts are $<30 \times 10^9/L$ (Provan, 2009); treatment is rarely indicated for patients with platelets $>30 \times 10^9/L$ unless they are undergoing a procedure likely to induce blood loss including surgery, dental extraction or childbirth (British Committee for Standards in Haematology General Haematology Task Force, 2003). Thrombopoietic agents have been extensively studied in ITP, and are increasingly used in patients with thrombocytopenia related to other chronic diseases.

Chronic Hepatitis C Virus (HCV) Infection

The global prevalence of chronic HCV infection is 130–170 million with an annual incidence of three to four million (WHO, 2013). A majority of HCV infected patients develop chronic liver disease making it a leading cause of cirrhosis and hepatocellular carcinoma worldwide.

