8.3.4. On label and off label definitions

If information on splenectomy, prior medication use, and contraindications for surgery is available, then use of eltrombopag for a patient will be categorized into the following groups:

- On-label use:
 - patient is an adult, has a diagnosis of chronic ITP, has been splenectomized or has a contraindication for surgery, and has received prior corticosteroids, immunoglobulins therapy; or
 - o patient is an adult, has a diagnosis of chronic HCV, has clinically meaningful thrombocytopenia limiting interferon-based therapy, and date of eltrombopag is after REVOLADE approval date (September 2013).
- Off-label use:
 - o patient is an adult, has chronic ITP, but has not received prior corticosteroids, immunoglobulins therapy or has not been splenectomized and does not have a contraindication for surgery;
 - o patient is an adult, has HCV, but does not have clinically meaningful thrombocytopenia limiting interferon-based therapy or the date of REVOLADE is prior to REVOLADE approval date;
 - o patient is an adult, but does not have ITP or HCV;
 - o patient is < 18 years of age

If there is no information on splenectomy, prior medication use, and contraindications for surgery, then classification will be more general:

- On-label use:
 - o patient is an adult and has a diagnosis of chronic ITP; or
 - o patient is an adult and has a diagnosis of HCV with clinically meaningful thrombocytopenia limiting interferon-based therapy, and date of eltrombopag after REVOLADE approval date
- Off-label use:
 - o patient is an adult, but has acute rather than chronic ITP;

- o patient is an adult, but does not have ITP and does not have HCV with clinically meaningful thrombocytopenia or has clinically meaningful thrombocytopenia limiting interferon-based therapy but date of eltrombopag is prior to REVOLADE approval date;
- o patient is an adult, but does not have ITP or HCV; or
- o patient is < 18 years of age

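### The on-label rule for adult chronic ITP needs a contraindication for surgery and a splenectomy status that the listed data items do not establish, so off-label use can be misclassified, in an unknown net direction

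*Protocol*

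**What the plan says.** **The rule.** Under Protocol section 8.3.4, use in an adult with chronic ITP is on-label if the patient "has been splenectomized or has a contraindication for surgery, and has received prior corticosteroids, immunoglobulins therapy". It is off-label if prior therapy is missing, or if the patient "has not been splenectomized and does not have a contraindication for surgery". This detailed rule applies when information on splenectomy, prior medication and contraindications is available. When there is none, a general rule makes every adult with chronic ITP on-label.

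**The data.** Section 8.3.2 lists two items that feed the surgery criterion: "Surgery (i.e., splenectomized or not" and "Comorbidities that may be contraindications for surgery (anemia, hyperbilirubinemia, neutropenia, leukopenia, pancytopenia, pneumonia, and others". Neither carries a date. For preceding and concomitant treatments the same section does ask for "Date of treatment initiation", and it also asks for dates of the diagnoses.

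**Related text.** Section 6.1 says of ITP that "If significant bleeding occurs there may be anemia proportional to the degree of bleeding", and that typically "the peripheral blood count reveals isolated thrombocytopenia and normal red cell and white cell indices". Section 8.7.1 plans a category of adults who have surgery during the observation period. Section 8.5.1 bases study size on the precision of the off-label proportion: 2.1 points at 5% with 400 patients.

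**The concern.** The rule asks whether surgery was contraindicated. The list asks only for conditions that might make it so, and the protocol does not say how one becomes the other. The proxy is also a poor one by the protocol's own account. Anemia can follow from ITP bleeding, and white-cell abnormalities do not belong to the typical ITP picture, so neither by itself shows that surgery was ruled out.

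For splenectomy the gap is one of timing. Observation can run for years (in Germany from April 2010 to September 2014, section 8.2.3), and section 8.7.1 foresees surgery within it. An undated status cannot separate a splenectomy that came before REVOLADE from one that came after.

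At stake is the proportion that sizes the study and that section 8.2.4 needs in order to judge prescribing against the label. The criterion acts on the main labelled group, because section 8.2.5 expects very few HCV patients. An SAP can add a mapping rule, but it cannot recover a chart entry or a date that was never abstracted.

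**Working it through.** **1. The plan's own figure.** Inputs from section 8.5.1: n = 400, p = 0.05, 95% confidence. Half-width = 1.96 × √(0.05 × 0.95 / 400) = 0.0214, giving limits of 0.0286 and 0.0714. This matches the stated 2.1 points and 2.9% to 7.1%. The other eleven half-widths in Table 1 reproduce in the same way.

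**2. Rule against data.**

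| What 8.3.4 needs | What 8.3.2 lists | Possible error |
|---|---|---|
| Splenectomised (no timing stated) | Splenectomised or not, no date | A splenectomy after the first dose meets the criterion; with prior therapy the use is on-label. Towards on-label only. |
| A contraindication for surgery | Comorbidities that might be contraindications, open list, no date | Broad reading: off-label patients become on-label. Strict reading, or a contraindication not charted as a comorbidity: on-label patients become off-label. |

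Reading the splenectomy criterion as meaning before the first dose does not help, because the listed item cannot apply that reading.

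**3. Illustration, errors towards on-label.** Let m be the share of truly off-label patients relabelled on-label. The documents give no value; 10% to 50% is an assumption. Observed share = p(1 − m), with p = 5% and n = 400:

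| m | Observed | Shift (points) |
|---|---|---|
| 10% | 5% × 0.90 = 4.5% | 0.5 |
| 25% | 5% × 0.75 = 3.75% | 1.25 |
| 40% | 5% × 0.60 = 3.0% | 2.0 |
| 50% | 5% × 0.50 = 2.5% | 2.5 |

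The shift equals the stated half-width at m = 2.1 / 5 = 42%.

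**4. Only some off-label patients are susceptible.** Patients under 18, those without ITP or HCV, and those without prior therapy stay off-label whatever the surgery items say. If a share s is susceptible, observed = p(1 − s·m). With s = 50% and m = 50%: 5% × 0.75 = 3.75%, a shift of 1.25 points, inside the stated precision.

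**5. Errors towards off-label.** Let c be the share of the cohort that is truly on-label through a contraindication, and g the share of these not captured (both assumed). Observed = p(1 − m) + c·g.
- m = 10%, c = 30%, g = 10%: 4.5% + 3.0% = 7.5%, above the true 5%.
- m = 40%, c = 10%, g = 10%: 3.0% + 1.0% = 4.0%, below it.

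The sign depends on quantities that the protocol does not give.

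**The case against.** A reader might infer that off-label patients are systematically turned into on-label ones. The documents do not support that. Nothing says that a listed comorbidity counts as a contraindication: 8.3.2 presents the list as possibilities, and 8.3.4 requires the contraindication itself. The mapping could be set in the SAP, which is not shown. Only the undated splenectomy errs in one direction.

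Other limits also stand:
- Section 8.3.2 is a summary list. The surgery category in 8.7.1 suggests that timing may be intended, although it is not listed.
- Hematologic malignancy and marrow failure are recorded separately with dates, so charted marrow disease would be visible. A mistaken ITP diagnosis is a different problem.
- Section 8.9 provides for standard scripts and abstractor training, and 8.8.1 for source data verification. Distortion between sites or countries is possible but not shown.
- The objectives in section 7 concern medical condition, age and patient characteristics. None of the patient categories in 8.7.1 uses the contraindication criterion.

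These points limit the claim about direction and size. They do not supply the missing items: scripts and verification check what is collected, and an SAP rule can act only on what is collected.

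**Conclusion.** The concern holds as a mismatch between the classification rule and the listed data. The surgery criterion in 8.3.4 has no matching contraindication item, no mapping rule and no splenectomy date. The splenectomy error runs towards on-label. The contraindication error can run either way, so the net effect on the off-label proportion is unknown.

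The size is illustrative only. At a true 5%, errors towards on-label alone would have to affect more than about two in five off-label patients before they outweighed the planned half-width, and then only if all off-label patients were susceptible. The planned confidence interval would not reveal an error of either sign. Confidence is high that the gap exists; the direction and size remain open.

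**What to change.** **Section 8.3.2.** Add an item on whether surgery is documented in the chart as contraindicated before the first REVOLADE dose (yes, no, not documented), with reason and date. Add the date of splenectomy.

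**Section 8.3.4.**
- Count the surgery criterion as met only if the splenectomy, or the documented contraindication, preceded the first dose.
- Keep the comorbidity list as descriptive data that does not by itself set label status.
- State how a patient is classified when only the contraindication is undocumented. The present text covers information available and no information, but not this mixed case. Without a rule such patients could drift into the general rule, which makes every adult with chronic ITP on-label. Showing them as a separate unclassifiable group is one way.
- Report the off-label proportion under a strict reading (documented contraindications only) and a broad reading (listed comorbidities also count).

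The classification would rest on what the treating physician recorded, so no clinical criterion is being proposed.

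**Cost.** A few more eCRF fields in charts already being abstracted, a short addition to 8.3.4, and a visible not-documented group in the tables. The change belongs before abstraction starts, since a later correction would mean reopening charts at 18 to 21 sites.
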